8.2.2. Cycle 17 Randomization Visit and Every 3 Cycles Thereafter

The following procedures will be performed on Day 1 (± 3 days) of Cycles 17 and every 3 cycles thereafter (unless indicated otherwise) until disease progression, unacceptable treatment-related toxicity, or other reasons outlined in [Section 9.2](#):

Pre-Dose

- Adverse events
- Concomitant medications
- Study drug compliance review
- Physical exam
- Vital signs
- ECOG
- Hematology
- Serum chemistry
- CT/MRI (Cycle 23, Cycle 29, Cycle 35, and then annually thereafter)
- Overall response assessment
- Bone marrow biopsy (± 14 days from C29 unless collected prior for CR assessment, and confirmed MRD-negative in BM)
- MRD assessment (by PB starting Cycle 20, 23, 26, 29, and every 6 cycles thereafter; by bone marrow aspirate [BMA] at Cycle 29 in randomized subjects, and in any subject with MRD-neg conversion in PB; BMA can be drawn ± 14 days from C29D1.)
- ██████████ assays ██████████

Post-Dose

- Dispense randomization specific study medication to subject for off-site use and provide study drug compliance instructions

8.2.3. Suspected MRD-positive Relapse Visit (Any Time)

If MRD-positive relapse is suspected, subject should return to clinic as soon as possible and the following procedures will be performed:

- Adverse events
- Concomitant medications
- Study drug compliance review
- Physical exam
- Vital signs
- ECOG
- Hematology
- Serum chemistry
- Overall response assessment
- MRD assessment (by PB)
- ██████████ assays

8.3. Fixed Duration Cohort

Fixed Duration Cohort: Treatment

The Schedule of Assessments ([Appendix B](#)) summarizes the frequency and timing of efficacy, ██████████ and safety measurements applicable to this study. The timing of all visits will be based on using Cycle 1 Day 1 (C1D1) as the anchor visit and all subsequent visits should use the C1D1 date as the basis for scheduling.

Following completion of the Screening visit and once eligibility has been confirmed (per inclusion/exclusion criteria), subjects will initiate ibrutinib treatment. Venetoclax will be added to ibrutinib treatment and initiated after completion of 3 cycles of ibrutinib. The venetoclax dose will be ramped up over 5 weeks per standard dosing recommendations (see [Section 5.3](#) for ibrutinib and venetoclax dosing).

After completion of 15 cycles of treatment, subjects will come off treatment and will continue to be followed for efficacy. Subjects that are unable to complete all 12 cycles of combination therapy will continue to follow the same visit schedule until disease progression. After disease progression, subjects will enter the Post-PD Follow up Phase ([Section 8.9](#)).

8.3.1. Treatment Visits

8.3.1.1. Cycle 1 Day 1 (C1D1) Visit

Pre-Dose

The following procedures will be performed prior to dosing (within 3 days) of the C1D1 Visit. Please note, C1D1 Visit procedures done at Screening will not need to be repeated **if done within 3 days of first dose with study drug**.

- Confirm eligibility (per inclusion/exclusion criteria) and enroll subject. Dosing should occur within 3 days of confirmation.
- Adverse events
- Physical examination
- Vital signs
- ECOG performance status
- Concomitant medications
- Hematology
- Serum chemistry (including creatinine clearance)
- β_2 -microglobulin
- Tumor Lysis Risk assessment (use Screening CT and C1D1 ALC. see [Appendix H](#) for risk assessment categories)
- ██████████ assays
- IGHV - will be derived from a ██████████ sample (if IGHV result is not informative for any reason, another peripheral blood sample should be drawn and sent to the central lab at the next appropriate timepoint)
- FISH panel
- Karyotype
- MRD in peripheral blood
- Perform urine pregnancy test for women of childbearing potential only

Dosing and Post First Dose

- In-clinic administration of ibrutinib
- Dispense ibrutinib for offsite use and provide study drug compliance instructions

8.3.1.2. Cycles 2 and 3 Visits

Pre-Dose

The following procedures will be performed on Day 1 (± 3 days) of each cycle (except for CT/MRI):

- Adverse events
- Concomitant medications
- Study drug compliance review
- Physical exam
- Vital signs
- ECOG
- CT/MRI (to assess response and lymph node sum of the product of the diameters [SPD] for TLS risk assessment, Cycle 3 only – to be obtained as close to the beginning of Cycle 4 as possible, while still allowing for appropriate TLS risk-guided interventions including hospitalization if appropriate)
- Hematology
- Serum chemistry

Dosing and Post-Dose

- In-clinic administration of ibrutinib (Cycle 2 only)
- Dispense ibrutinib for offsite use and provide study drug compliance instructions

8.3.1.3. Cycle 4 Visits

8.3.1.3.1. Pre-Cycle 4 (Pre-initiation of Venetoclax)

The following procedures will be performed 2-3 days (± 3 days) prior to Cycle 4:

- Overall response assessment
- Hematology
- Serum Chemistry
- ██████████ assays ██████████
- Tumor Lysis Risk assessment (see [Appendix H](#) for risk assessment categories)
- Tumor Lysis Syndrome prophylaxis (see [Section 5.4.2.2](#) for prophylaxis schedule based on risk)

The following procedures will be performed 1 day prior to Cycle 4:

- Tumor Lysis Syndrome prophylaxis (see [Section 5.4.2.2](#) for prophylaxis schedule based on risk)

8.3.1.3.2. Cycle 4 Week 1 Day 1

Pre-Dose

The following procedures will be performed on Day 1 (± 3 days) of Cycle 4, Week 1:

- Adverse events
- Concomitant medications
- Study drug compliance review
- Physical exam
- Vital signs
- ECOG
- Hematology
- Serum chemistry
- Creatinine clearance (Cockcroft-Gault)
- Tumor Lysis Risk assessment (see [Appendix H](#) for risk assessment categories)
- Tumor Lysis Syndrome prophylaxis (see [Section 5.4.2.2](#) for prophylaxis schedule based on risk, venetoclax administration setting, and frequency of serum chemistry monitoring assessments)

Dosing and Post First Dose of Venetoclax

- In-clinic administration of ibrutinib
- In-clinic administration of venetoclax 20 mg for low and medium risk TLS subjects
- Consider hospitalization for first dose of venetoclax 20 mg in medium risk TLS subjects with a CrCl < 80 mL/min
- In-hospital administration of first dose of venetoclax 20 mg for high risk TLS subjects
- Dispense ibrutinib and venetoclax for offsite use and provide study drug compliance instructions

8.3.1.3.3. Cycle 4 Week 1 Day 2

Pre-Dose

- Adverse events
- Hematology
- Serum chemistry
- Tumor Lysis Syndrome prophylaxis (see [Section 5.4.2.2](#) for prophylaxis schedule based on risk and frequency of serum chemistry monitoring assessments)

8.3.1.3.4. Cycle 4 (Week 2 – Week 4) Visits

The following procedures will be performed on Day 1 (± 3 days) of Cycle 4, Weeks 2, 3, and 4 (coincides with venetoclax standard dose ramp-up of 50 mg (W2D1), 100 mg (W3D1), and 200 mg (W4D1):

Pre-Dose

- Adverse events
- Concomitant medications
- Study drug compliance review
- Physical exam
- Vital signs
- ECOG
- Hematology
- Serum chemistry
- Creatinine clearance (Cockcroft-Gault)
- Tumor Lysis Syndrome Risk assessment (see [Appendix H](#) for risk assessment categories)
- Tumor Lysis Syndrome prophylaxis (see [Section 5.4.2.2](#) for prophylaxis schedule based on risk and frequency of serum chemistry monitoring assessments)

Dosing and Post-Dose

- In-clinic administration of venetoclax 50 mg (Week 2), 100 mg (Week 3) and 200 mg (Week 4) for low and medium TLS risk subjects
- Consider hospitalization for first dose of venetoclax 50 mg in medium risk TLS subjects with a CrCl < 80 mL/min
- In-hospital administration of first dose of venetoclax 50 mg dose at Week 2 for high risk TLS subjects; in-clinic administration of venetoclax 100 mg (Week 3) and 200 mg (Week 4) for high risk TLS subjects
- Dispense venetoclax for offsite use and provide study drug compliance instructions

8.3.1.3.5. Cycle 4 Week 2 Day 2

Pre-Dose

- Adverse events
- Hematology
- Serum chemistry
- Tumor Lysis Syndrome prophylaxis (see [Section 5.4.2.2](#) for prophylaxis schedule based on risk and frequency of serum chemistry monitoring assessments)

8.3.1.4. Cycle 5 Visits

8.3.1.4.1. Cycle 5 Week 1 and Week 3 Visits

Pre-Dose

The following procedures will be performed on Day 1 (± 3 days) of Cycle 5, Week 1, and Week 3:

- Adverse events
- Concomitant medications
- Study drug compliance review
- Physical exam
- Vital signs
- ECOG
- Hematology
- Serum chemistry
- Creatinine clearance (Cockcroft-Gault)
- Tumor Lysis Syndrome Risk assessment (see [Appendix H](#) for risk assessment categories) (Week 1 Only)
- Tumor Lysis Syndrome prophylaxis (see [Section 5.4.2.2](#) for prophylaxis schedule based on risk, venetoclax administration setting, and frequency of serum chemistry monitoring assessments) (Week 1 Only)

Dosing and Post-Dose

- In-clinic administration of venetoclax
- Dispense ibrutinib and venetoclax for offsite use and provide study drug compliance instructions (Week 1 only)

8.3.1.5. Cycle 6 – Cycle 9 Visits

Pre-Dose

The following procedures will be performed on Day 1 (± 3 days) of Cycles 6, 7, 8, and 9:

- Adverse events
- Concomitant medication
- Study drug compliance review
- Physical exam
- Vital signs
- ECOG

- Hematology
- Serum chemistry
- CT/MRI (Cycle 7 only)
- Overall response assessment (Cycle 7 only)
- MRD assessment (in peripheral blood Cycle 7 only)

Dosing and Post-Dose

- Dispense ibrutinib and venetoclax for offsite use and provide study drug compliance instructions

8.3.1.6. Cycle 10 and Cycle 13 Visits

Pre-Dose

The following procedures will be performed on Day 1 (± 3 days) of Cycles 10 and 13:

- Adverse events
- Concomitant medications
- Study drug compliance review
- Physical exam
- Vital signs
- ECOG
- Hematology
- Serum chemistry
- b₂-microglobulin (at Cycle 10 only)
- CT/MRI (C10 and C13)
- Overall response assessment (by imaging C10 and C13)
- MRD assessment (in peripheral blood)
- Bone marrow aspirate and biopsy (C10). Bone marrow MRD should be assessed whenever a BM aspirate is collected. Bone marrow can be collected ± 14 days from scheduled C10D1.

Post-Dose

- Dispense ibrutinib and venetoclax for offsite use and provide study drug compliance instructions

8.3.2. Fixed Duration Cohort: Post treatment visits

For subjects who complete all 15 cycles of fixed duration regimen, the following procedures will be performed on Day 1 (± 3 days) of Cycles 19 (Post Completion of Cycle 15 therapy), 25, 28, 31, and every 6 months thereafter (or as indicated below) until disease progression, unacceptable treatment-related toxicity, or other reasons outlined in [Section 9.2](#).

Subjects who discontinue treatment before completing the fixed duration regimen will continue to come in for response follow-up visits per schedule until confirmed disease progression.

- Physical exam
- Vital signs
- ECOG
- Hematology
- Serum chemistries
- CT/MRI (Cycle 19, Cycle 25, Cycle 31, and annually thereafter)
- Overall response assessment
- MRD assessment (by PB at Cycle 19, 25, 28*, 31, and annually thereafter; by PB and BMA at Cycle 19; BMA can be drawn ± 14 days from C19D1) :
- Bone Marrow Biopsy (Cycle 19 only)
- ██████████ assays ██████████
- * NOTE: Cycle 28 MRD collection is not required for patients who have completed these respective visits prior to Amendment 3 site approval and any required re-consent

8.4. Reintroduction of Study Drug (MRD and FD Cohorts)

Subjects in the MRD cohort who are randomized and subjects in the Fixed Duration cohort who complete the fixed duration treatment may have study drug reintroduced if they become MRD positive (MRD cohort) or have confirmed progressive disease (either cohort). See [Section 5.4.2.2](#), and [Section 7.1.1.10](#) for TLS risk assessment and prophylaxis, respectively

Imaging for restaging is required prior to reintroduction. Medical Monitor approval is required prior to reintroduction of any study drug.

Creatinine clearance, Coagulation panel (PT/INR, aPTT) (for ibrutinib reintroduction), IGHV, karyotype, FISH, and ██████████ will be assessed at the first reintroduction visit. Prior to reintroduction, ECG and Echo/MUGA will be obtained, and cardiology consultation prior to reintroduction should be considered for patients with cardiac comorbid conditions or significant cardiac risk factors. The following procedures will be performed prior to reintroduction, and every 4 months for the first year, then every 6 months until PD, unless otherwise indicated.

- Physical exam
- Vital signs and Weight

- ECOG
- Hematology
- Serum chemistry
- CT/MRI (refer to [Appendix D](#) and [Appendix E](#) for specific timepoints)
- Overall response assessment Adverse events
- Concomitant medications
- Study drug compliance review
- Bone Marrow assessment (only at visit if needed to confirm CR, or if clinically indicated to confirm PD)
- ██████████ Assay ██████████
- ECG (prior to reintroduction then as clinically indicated)
- Echocardiogram or MUGA scan (prior to reintroduction to allow sufficient time for subsequent evaluation and clinical decision making, and then as clinically indicated)

Subjects will follow the schedule for their retreatment as outlined in [Appendix C](#), [Appendix D](#), and [Appendix E](#). Retreatment with ibrutinib or venetoclax or combination can be continued for the duration indicated, until disease progression as determined by investigator or until they meet criteria for withdrawal in [Section 9.2](#). Subjects must meet all of the criteria for reintroduction listed below. Per investigator discretion and in communication with medical monitor, initiation of reintroduction can be delayed until indication for treatment per IWCLL criteria is present.

Criteria for Reintroduction of Study Drug

Inclusions

1. ECOG Performance Status ≤ 2
2. Platelet count $>30,000/\mu\text{L}$ ($30,000 \text{ cells}/\text{mm}^3$ or $30 \times 10^9/\text{L}$)
3. Adequate hepatic and renal function defined as:
 - a) Serum aspartate transaminase (AST) or alanine transaminase (ALT) $\leq 3.0 \times$ upper limit of normal (ULN)
 - b) Creatinine Clearance (CrCl) $\geq 60 \text{ mL}/\text{min}$ (eg, as estimated by Cockcroft-Gault)
 - c) Bilirubin $\leq 1.5 \times$ ULN (unless bilirubin rise is due to Gilbert's syndrome or of non-hepatic origin)
4. Prothrombin time (PT)/International normal ratio (INR) $< 1.5 \times$ (upper limit of normal) ULN and PTT (activated partial thromboplastin time [aPTT]) $< 1.5 \times$ ULN (unless abnormalities are unrelated to coagulopathy or bleeding disorder).
5. Female subjects of reproductive potential must have a negative serum pregnancy test upon study entry.
6. Male and female subjects of reproductive potential who agree to use both a highly effective method of birth control (eg, implants, injectables, combined oral contraceptives, some

intrauterine devices [IUDs], complete abstinence³, or sterilized partner) and a barrier method (eg, condom, cervical ring, sponge, etc.) during the period of therapy and for 90 days after the last dose of study drug. Male subjects must agree to refrain from sperm donation until 90 days after the last dose of study drug.

Exclusions

1. Development of other malignancies, except:
 - a) Malignancy treated with curative intent and with no known active disease present and felt to be at low risk for recurrence by the treating physician
 - b) Adequately treated non-melanoma skin cancer or lentigo maligna without evidence of disease
 - c) Adequately treated carcinoma in situ without evidence of disease
2. Known or suspected history of Richter's transformation.
3. Recent infection requiring systemic treatment that is ongoing or any uncontrolled active systemic infection.
4. History of stroke or intracranial hemorrhage within 6 months prior to enrollment.
5. Any life-threatening illness, medical condition, or organ system dysfunction that, in the investigator's opinion, could compromise the subject's safety.
6. Currently active, clinically significant cardiovascular disease, such as uncontrolled arrhythmia or Class 3 or 4 congestive heart failure as defined by the New York Heart Association Functional Classification; or a history of myocardial infarction, unstable angina, or acute coronary syndrome within 6 months.
7. Requires treatment with a strong cytochrome P450 (CYP) 3A inhibitor (see [Appendix G](#)).
8. Currently active, clinically significant hepatic impairment Child-Pugh Class B or C according to the Child Pugh classification ([Appendix K](#)).
9. Uncontrolled autoimmune hemolytic anemia or idiopathic thrombocytopenia purpura, or the need for daily prednisone >20 mg daily (or corticosteroid equivalent) to treat or control the autoimmune disease.

³ Complete abstinence is a highly effective method only if defined as refraining from heterosexual intercourse during the entire period of risk associated with the study treatments. The reliability of sexual abstinence needs to be evaluated in relation to the duration of the clinical trial and the preferred and usual lifestyle of the subject.

http://www.hma.eu/fileadmin/dateien/Human_Medicines/01_About_HMA/Working_Groups/CTFG/2014_09_HMA_CTFG_Contraception.pdf

Categories of Reintroduction

Ibrutinib: Appendix C

- Subjects in the MRD cohort who are MRD-negative and have been randomized to placebo; OR
- Subjects in the Fixed Duration cohort who have completed the fixed duration of treatment.

Venetoclax: Appendix D

- Subjects in the MRD cohort who are MRD-positive and have been randomized to ibrutinib only; OR
- Subjects in the MRD cohort who are in MRD-negative arms and have previously had ibrutinib reintroduced.

Ibrutinib + venetoclax: Appendix E

- Subjects in the Fixed Duration cohort who have completed the fixed duration of treatment (subjects will take combination for the same fixed duration in the protocol [15 months]).

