12. Major surgery within 4 weeks of first dose of study drug.
13. Any life-threatening illness, medical condition, or organ system dysfunction that, in the investigator's opinion, could compromise the subject's safety or put the study outcomes at undue risk.
14. Currently active, clinically significant cardiovascular disease, such as uncontrolled arrhythmia or Class 3 or 4 congestive heart failure as defined by the New York Heart Association Functional Classification; or a history of myocardial infarction, unstable angina, or acute coronary syndrome within 6 months prior to enrollment.
15. Unable to swallow capsules/tablets or malabsorption syndrome, disease significantly affecting gastrointestinal function, or resection of the stomach or small bowel, symptomatic inflammatory bowel disease or ulcerative colitis, or partial or complete bowel obstruction.
16. Concomitant use of warfarin or other vitamin K antagonists.
17. Requires treatment with a strong cytochrome P450 (CYP) 3A inhibitor (see [Appendix G](#)).
18. Currently active, clinically significant hepatic impairment Child-Pugh Class B or C according to the Child Pugh classification ([Appendix K](#)).
19. Lactating or pregnant.
20. Unwilling or unable to participate in all required study evaluations and procedures.
21. Unable to understand the purpose and risks of the study and to provide a signed and dated informed consent form (ICF) and authorization to use protected health information (in accordance with national and local subject privacy regulations).
22. Uncontrolled autoimmune hemolytic anemia or idiopathic thrombocytopenia purpura, such as those subjects with a declining hemoglobin level or platelet count secondary to autoimmune destruction within the 4 weeks prior to first dose of study drug, or the need for daily prednisone >20 mg daily (or corticosteroid equivalent) to treat or control the autoimmune disease.

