7.1.2.6. Pregnancy Test

Serum pregnancy test will be required at Screening by local laboratory only for women of childbearing potential. A urine pregnancy test will also be performed on Day 1 prior to first dose. If positive, pregnancy must be ruled out by ultrasound to be eligible. This test may be performed more frequently if required by local regulatory authorities.

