8.2.1. Treatment Visits

8.2.1.1. Cycle 1 Day 1 (C1D1) Visit

Pre-Dose

The following procedures will be performed prior to dosing (within 3 days) of the C1D1 Visit. Please note, C1D1 Visit procedures done at Screening will not need to be repeated **if done within 3 days of first dose with study drug.**

- Confirm eligibility (per inclusion/exclusion criteria) and enroll subject. Dosing should occur within 3 days of confirmation.
- Adverse events
- Physical examination
- Vital signs
- ECOG performance status
- Concomitant medications
- Hematology
- Serum chemistry (including creatinine clearance)
- Tumor Lysis Risk assessment (use Screening CT and C1D1 ALC. see [Appendix H](#) for risk assessment categories)
- XXXXXXXXXX
- IGHV (if IGHV sample is not informative for any reason, another peripheral blood sample should be drawn and sent to the central lab at the next appropriate timepoint)
- FISH panel
- Karyotype
- Buccal Swab
- MRD in peripheral blood
- Perform urine pregnancy test for women of childbearing potential only

Dosing and Post First Dose

- In-clinic administration of ibrutinib
- Dispense ibrutinib for offsite use and provide study drug compliance instructions

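### Two criteria for restarting study drug (recent stroke or intracranial haemorrhage, negative pregnancy test) still refer to study entry, so they exclude no one at restart, and no restart pregnancy test is scheduled

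*Protocol*

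**What the plan says.** Protocol section 8.4 governs restarting study drug in both cohorts. The list is binding: "Subjects must meet all of the criteria for reintroduction listed below". In addition, "Medical Monitor approval is required prior to reintroduction of any study drug".

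Two items on the list refer to the original entry into the study:

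- Exclusion 4: "History of stroke or intracranial hemorrhage within 6 months prior to enrollment". This is identical to entry exclusion 10 in section 4.2.
- Inclusion 5: "Female subjects of reproductive potential must have a negative serum pregnancy test upon study entry". The same sentence appears in entry inclusion 9 in section 4.1.

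Enrollment is a dated step. Section 8.2.1.1 places it at Cycle 1 Day 1: "Confirm eligibility (per inclusion/exclusion criteria) and enroll subject. Dosing should occur within 3 days of confirmation". Section 8.3.1.1 says the same for the Fixed Duration (FD) cohort.

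On testing, section 7.1.2.6 states: "Serum pregnancy test will be required at Screening by local laboratory only for women of childbearing potential". It adds a urine test on Day 1 before the first dose, and further tests only where local regulators require them.

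**The concern.** A criterion for restarting a drug should describe the subject at the restart. These two describe the subject at first entry, more than a year earlier. Anyone on study had already met both, so a site that applies the text literally will pass every subject on both items.

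Two hazards the protocol itself recognises are at stake. Section 1.2.4.2 lists major haemorrhage under ibrutinib, some of it fatal and including intracranial bleeding. Section 5.4.2.10 warns of embryo-fetal harm with venetoclax, and section 1.2.1.2 reports malformations in rats and rabbits given ibrutinib. The 6-month stroke rule and the pregnancy test protected subjects at first dosing. Neither operates at re-dosing.

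**Working it through.** The plan gives no figure to reproduce. The check compares texts and calculates elapsed time.

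**Step 1. Was the wording meant to refer to entry?** Compare the neighbouring criteria at entry and at reintroduction.

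- Cardiac events. Entry exclusion 14 ends "or acute coronary syndrome within 6 months prior to enrollment". Reintroduction exclusion 6 ends "or a history of myocardial infarction, unstable angina, or acute coronary syndrome within 6 months", with the enrollment reference removed.
- Other malignancies. The entry rule's 3-year disease-free interval before first dose is dropped at reintroduction.
- Autoimmune cytopenias. The entry rule's 4-week window before first dose is dropped at reintroduction.
- Stroke or intracranial haemorrhage, and the pregnancy test. Unchanged.

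The list was adapted for restart and these two items were missed. A stroke rule in a restart list has no purpose unless it looks back from the restart.

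**Step 2. Can the written window reach the period before restart?** Inputs: 28-day cycles (SAP 1.1). FD restart requires completion of 15 cycles (Protocol 8.4). MRD-cohort restart requires randomization, with randomized treatment starting at Cycle 17 Day 1 (SAP 1.1). A repeat of ibrutinib + venetoclax in the FD cohort requires more than 2 years to progression after the regimen (Protocol 3.1.3). One month is taken as 30.44 days.

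| Restart | Earliest time after Cycle 1 Day 1 | Months | Start of a 6-month look-back from restart |
|---|---|---|---|
| FD, ibrutinib alone | 15 × 28 = 420 days | 420 / 30.44 = 13.8 | 13.8 − 6 = 7.8 months after enrollment |
| MRD cohort | 16 × 28 = 448 days | 448 / 30.44 = 14.7 | 14.7 − 6 = 8.7 months |
| FD, ibrutinib + venetoclax | more than 420 + 730 = 1,150 days | more than 37.8 | more than 37.8 − 6 = 31.8 months |

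The written window ends at enrollment (month 0). The relevant window starts at month 7.8 at the earliest, so the two never overlap. If exclusion 4 were tied to the restart dose, a restart at day 420 would screen for events from about day 237 (420 − 6 × 30.44) to day 420.

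**Step 3. Does anything else call for a pregnancy test at restart?**

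- Section 7.1.2.6 names Screening and Day 1 only. By contrast, section 7.1.2.3 schedules coagulation tests at both Screening and reintroduction.
- The procedure list in section 8.4 contains no pregnancy test.
- Appendices A and B have a pregnancy row, and their local-laboratory footnotes name pregnancy tests. The visible rows of Appendices C, D and E have none, and the local-laboratory footnotes of C and E omit it. Appendix D has no such footnote.
- Entry exclusion 19, which covers pregnancy and lactation, was not carried into the reintroduction exclusions.

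**Step 4. Who is outside the contraception duty?** Contraception (section 4.1, inclusion 10) and pregnancy reporting (section 11.4.4) run to 90 days after the last dose. For an FD completer they lapse at about 420 + 90 = 510 days (16.8 months). Before a repeat of ibrutinib + venetoclax she will have spent more than 730 − 90 = 640 days (21 months) outside them. MRD-cohort subjects are generally still taking ibrutinib or blinded capsules and remain bound.

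**The case against.** The strongest reply is that no sensible investigator would apply a restart checklist to a date more than a year past. Under the heading of reintroduction criteria, both items would naturally be read as applying now, and inclusion 5 would then itself require a test. That may well be how many sites act. But the protocol defines enrollment as the Cycle 1 Day 1 step, and even the generous reading leaves no scheduled pregnancy test.

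The second reply is that other safeguards exist. For stroke, exclusion 5 allows refusal on the investigator's opinion, the Medical Monitor must approve, and section 8.4 calls for review of adverse events and concomitant medications and a physical examination before restart. A recent intracranial bleed is unlikely to go unnoticed. This stands, and it limits the stroke part to the loss of a stated 6-month rule, replaced by judgement. It is also fair that MRD-cohort subjects who add venetoclax to continuing ibrutinib are exposed to ibrutinib regardless. The stroke rule therefore matters mainly for placebo-arm and FD restarts.

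For pregnancy, a known case is covered by sections 9.2 and 11.4.4, and reintroduction inclusion 6 renews contraception. Neither detects a pregnancy that no one yet knows about. The group is small: section 1.1.1 puts the median age at diagnosis at about seventy, and the usual FD restart is ibrutinib alone, whereas the warning in section 5.4.2.10 concerns venetoclax.

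Finally, the absence of a row in Appendices C to E is imperfect evidence. Some rows are redacted, and D and E carry MRD footnotes with no visible row. The schedule point therefore rests mainly on section 7.1.2.6 and the footnotes of C and E.

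**Conclusion.** The point holds. As written, reintroduction exclusion 4 and inclusion 5 cannot exclude anyone who was properly enrolled, because both were settled at entry, at least 420 days before any restart. This assumes that enrollment and study entry carry their ordinary meaning in the protocol and that entry criteria were applied without deviation. Days 420 and 448 are floors. Real restarts come later, since confirmed progression or confirmed MRD-positive relapse must come first.

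For stroke and intracranial haemorrhage, a fixed 6-month rule has been replaced by case-by-case judgement. For pregnancy, no scheduled test would find an unrecognised pregnancy before re-exposure, and the exposed group is chiefly FD women beyond 90 days from their last dose. The documents do not give the number of women of reproductive potential; entry age is 18 to 70. The inclusion 5 reference is strictly to Screening (serum), with a urine test on Day 1, which does not change the conclusion.

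This is a participant-safety defect, partly mitigated and cheap to correct. It does not touch any endpoint, alpha or power.

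**What to change.** At the next amendment:

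- Exclusion 4 in section 8.4: count the 6 months back from the first dose of reintroduced study drug.
- Inclusion 5 in section 8.4: require a negative serum pregnancy test before the first dose of reintroduced study drug.
- Add that test to section 7.1.2.6 and to the first visit in Appendices C, D and E, following the model of section 7.1.2.3 for coagulation.

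The cost is a few lines of text and one local pregnancy test for each woman of reproductive potential who restarts. The change to exclusion 4 needs no new procedure. Section 3.1 plans about 10 years of follow-up for the FD cohort, so later restarts could still benefit.
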